9.3.2 Planned Sub-group Analyses

Sub-group analyses may require adjustment for prognostic imbalances, as the effect of randomization may not be preserved.

Gender analysis: A sub-group analysis is planned by gender as effect of exercise may vary by gender.

Physical activity level: A subgroup analysis is planned by quartiles of baseline physical activity level as measured by accelerometry at baseline. Level of baseline physical activity may modify the effect of the intervention and is an important potential confounder.

On protocol analysis: Non-adherence to the exercise intervention may modify the effect of the intervention and is an important potential confounder. Therefore, a pre-specified analysis of the primary outcome will be performed "on protocol", defined by adherence to

intervention protocol as defined by completion of 70% or greater of exercise sessions during the intervention period.

9.3.3 Secondary Outcomes and Analyses

We will repeat the primary outcome analyses that compared change in DSI from baseline to 12 weeks between groups, instead looking at change from baseline to 26 weeks and 52 weeks.

Change in EQVAS over time will be compared between study groups using Student's T-test. As well, we will compare the difference in proportion of individuals who develop new deficits (score of 2 or 3) in each domain of the EQ5D-5L over time. The degree to which change in symptom burden correlates with change in EQVAS will be assessed using Spearman and Pearson's correlation coefficients as indicated based on distribution of the data. Change in all other secondary outcomes over time will be compared between groups using the appropriate parametric and non-parametric statistical tests depending on data type and distribution. Bonferroni adjustments will be made for secondary outcomes to adjust for multiple study timepoints. Hospitalization will be analyzed using Poisson regression. For all analyses, two-sided p < 0.01 will be statistically significant. Statistical analysis will be performed using SAS 9.3 (Carey, NC).

We will validate the Godin Shepard Leisure-Time Exercise Questionnaire using accelerometry data. Correlation between Godin Questionnaire Score and active minutes (light, moderate and moderate-vigorous activity) measured by accelerometry at each study assessment time point will be assessed using Pearson or Spearman correlation depending on distribution of the data. Internal consistency of the Godin questionnaire will be assessed using Cronbach alpha and Intraclass Correlation Coefficient. In those individuals in which active minutes measured using accelerometry did not change between assessment periods (change of less than 10% from baseline), test re-test reliability of the Godin Questionnaire will be assessed using Kappa statistic. Responsiveness will be modelled using linear regression with Godin questionnaire score as the primary predictor of active minutes measured by accelerometry. Additional predictors including sex, age, diabetes and other comorbidities will be added to the model as sample size will allow.

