Study Endpoints Primary, Secondary and Mechanistic	Primary outcome: Change in symptom burden over time (12 weeks) as measured by Dialysis Symptom Index (DSI) severity score. Secondary outcomes: Change in generic health-related quality of life over time (12, 26, 52 weeks) as measured by EuroQol 5D-5L and EuroQol visual analogue scale Change in: modified symptom burden (modified DSI severity score); time for recovery post-HD; frailty status (Fried criteria); physical activity level (accelerometer and Godin-Shephard Leisure Time Physical Activity Questionnaire); exercise capacity (Incremental Shuttle Walk Test); self-

	efficacy for exercise (Self-Efficacy for Exercise Questionnaire; hospitalization rate (number hospital days admitted/patient year); all cause 1 year mortality
Brief Summary of Analysis	Sample size : The following assumptions were made: alpha 0.05; power 0.80; 30% dropout and 25% absolute difference in proportion of individuals in whom DSI severity score decreases by 7 points or more (minimal clinically important difference). Therefore, assuming a baseline symptom prevalence of 50% of individuals in each study group, 150 patients (75 in each arm) will be randomized and we will be able to detect a 25% reduction in the primary outcome.
	Primary analysis : Intention-to-treat, available-case basis, in the intervention versus control arm, using Chi-square test and logistic regression for categorical outcomes and t-tests/MannWhitney U for continuous outcomes.
	Secondary outcomes : Descriptive statistics, Kaplan Meier analysis, Poisson regression and linear mixed modeling and will be used as appropriate.

SCHEMATIC OF THE STUDY DESIGN

Enrolment and consent: Once informed consent is obtained, the Dialysis Symptom Index (DSI) will be administered to all participants. Those who score 0 on the DSI (no symptoms) will be deemed ineligible for the study

Randomization: To avoid bias, randomization will be performed following the baseline assessment.

Intervention phase: Participants in "intervention" group will receive study intervention during this time.

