9.3 Description of Statistical Methods

9.3.1 Primary Outcome

Developed in consultation with a statistician ([name], Chronic Disease Innovation

Centre) familiar with RCTs and our study outcomes, analysis will be performed in an intention-to-treat manner on a case available basis. Change in DSI severity score from baseline to 12 weeks will be compared between groups by independent two-tailed t-test or Mann-Whitney U test depending on distribution and using generalized linear mixed models with study timepoint as a random effect and adjusted for baseline DSI score. In a subgroup of individuals whose baseline DSI score is >7, the proportion of individuals whose DSI severity score has improved by 7 or more points from baseline to 12 weeks will be compared between groups at each study time point using Chi-square test.

Multiple logistic regression will be performed to determine predictors of a >7 point change in DSI severity score over time and adjusted for time varying confounders using a marginal structural model. Interaction terms for sex and baseline DSI score will also be inputted into the model. Although study group will be the primary predictor in this model, other key predictors of symptom burden (including baseline DSI score, diabetes status, ischemic heart disease (IHD), age, gender, race, smoking status, serum albumin level, hemoglobin, baseline physical function, physical activity level and interaction terms for gender/intervention and baseline DSI score/intervention) will also be tested in a step-wise manner.

If **missing outcome data** is greater than anticipated (25%) we will impute them according to current FDA/NAS/NRC recommendations using multiple imputation with chained equations ⁸⁶⁻⁸⁸. Specifically, multiple imputation creates 20-40 complete datasets with plausible values from the model-based predictive distributions, and pooled estimates and standard errors are obtained through the use of Rubin's combining rules. These models are predicated on the assumption that the data are missing at random (MAR). Finally, the robustness of the inferences about treatment effects to violations of the MAR assumptions will be evaluated through a sensitivity analysis ⁸⁸.

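### Change in EQ-VAS is compared by an unadjusted t-test although baseline EQ-VAS is collected; the test is valid but gives up precision that a baseline covariate would recover.

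*Combined protocol and SAP*

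**What the plan says.** **EQ-VAS.** Section 4.2.2 makes generic quality of life, measured by EQ-5D-5L and EQ-VAS, the principal secondary outcome. Section 9.3.3 gives the EQ-VAS test: "Change in EQVAS over time will be compared between study groups" by Student's t-test. No covariate is named. Sections 7.2 and 7.3 schedule EQ-VAS at baseline (Visit 1) and at 12, 26 and 52 weeks, so the baseline value will be available.

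**Synopsis.** The Brief Summary of Analysis gives, under primary analysis, "t-tests/MannWhitney U for continuous outcomes". For secondary outcomes it lists "Descriptive statistics, Kaplan Meier analysis, Poisson regression and linear mixed modeling and will be used as appropriate". It ties mixed modelling neither to EQ-VAS nor to a baseline covariate.

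**DSI.** Section 9.3.1 plans two analyses of mean change. Change "will be compared between groups by independent two-tailed t-test or Mann-Whitney U test depending on distribution", and it is also analysed "using generalized linear mixed models with study timepoint as a random effect and adjusted for baseline DSI score". The text does not say which of the two leads. Section 9.3.3 repeats the DSI analyses at 26 and 52 weeks.

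**The concern.** The plan accepts baseline adjustment for DSI but does not carry it to EQ-VAS, another repeated self-reported score with a baseline measurement. A change score subtracts the whole baseline value. When r is below 1, that subtracts more than the baseline predicts. It adds baseline measurement noise to the comparison and over-corrects any chance imbalance between arms: with equal variances, a baseline difference of d shifts the change-score estimate by (1−r)d in the opposite direction. ANCOVA subtracts only the part of the baseline that predicts follow-up.

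At stake is the power of the principal secondary comparison. Section 9.2 states its EQ-VAS power for all 75 patients per arm, while the same section expects 30% dropout, so there is little margin to lose.

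**Working it through.** **1. The plan's own figure.** Section 9.2 claims 80% power at alpha 0.05 for a 12-point EQ-VAS difference with 75 per arm. It gives no SD, so the claim cannot be reproduced. It can be solved for the SD of change it implies:

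SD = 12 / [(1.960 + 0.842) × √(2/75)] = 26.2.

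**2. Relative variance.** Let both visits have variance s², with correlation r.

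- Change score: Var = 2s²(1−r).
- ANCOVA: Var = s²(1−r²).
- Ratio: (1−r²) / [2(1−r)] = (1+r)/2.

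The documents give no r for EQ-VAS, so 0.3 to 0.8 is assumed. The extra patients that the change score needs for equal precision are 1/ratio − 1. The number per arm under ANCOVA that matches 75 under the t-test is 75 × ratio, rounded up.

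| r | Ratio | Variance reduction | Extra patients for change score | ANCOVA n matching 75 |
|---|---|---|---|---|
| 0.3 | 0.65 | 35% | 54% | 49 |
| 0.5 | 0.75 | 25% | 33% | 57 |
| 0.7 | 0.85 | 15% | 18% | 64 |
| 0.8 | 0.90 | 10% | 11% | 68 |

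**3. Effect on EQ-VAS power.** This uses the implied SD of 26.2, multiplied by √((1+r)/2) for ANCOVA, in the normal approximation at two-sided alpha 0.05. After 30% dropout, 75 × 0.70 = 52.5 per arm remain.

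| Per arm | t-test | ANCOVA, r = 0.3 | r = 0.5 | r = 0.7 | r = 0.8 |
|---|---|---|---|---|---|
| 75 | 80.0% | 93.5% | 89.9% | 86.0% | 84.0% |
| 52.5 | 65.0% | 82.8% | 77.2% | 72.0% | 69.5% |

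Section 9.3.1 anticipates 25% missing outcome data, which would leave 75 × 0.75 = 56 per arm, between the two rows. Section 9.3.3 sets p < 0.01 as the threshold for all analyses, which differs from the alpha used for sizing. At 0.01 and 52.5 per arm, the t-test has 40.8% power, against 55.2% for ANCOVA at r = 0.5. That mismatch of thresholds is a separate matter.

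**4. DSI.** Section 4.2.1 gives a pilot SD of 30 (n = 18), and Section 9.2 uses an SD of 16 for mean change. If both describe one population with equal variances at the two visits, then 16² = 2 × 30² × (1−r), so

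r = 1 − 256/1800 = 0.86, and (1+r)/2 = 0.93.

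The variance saving is about 7%, equal to about 8% more patients. The pilot is small, so 0.86 is uncertain, but it is the only indication in the documents.

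**5. What sized the trial.** The 58 per arm in Section 9.2 comes from responder rates of 50% and 25%; a two-proportion calculation at 80% power reproduces it. The (1+r)/2 formula concerns means and does not apply to that comparison.

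**The case against.** **A change-score t-test is a legitimate analysis.** This stands. Randomisation makes it unbiased with correct type I error. A reader might infer that the EQ-VAS result would be biased or invalid; nothing in the design supports that.

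**The synopsis allows mixed modelling for secondary outcomes, which could cover EQ-VAS.** This stands only in part. The phrase is general, names neither EQ-VAS nor a baseline term, and leaves the choice open. Section 9.3.3 is the specific instruction, and it names Student's t-test.

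**DSI is already adjusted.** This stands. A reader might infer from the synopsis that mean DSI change is also analysed only without adjustment. Section 9.3.1 plans a model adjusted for baseline DSI, and Section 9.3.3 carries it to 26 and 52 weeks. A brief synopsis that omits a model given in the body does not show that precision is lost. What remains is that the two analyses are unranked and the synopsis does not match the body.

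**The size is unknown.** This stands as a caution. No correlation is given for EQ-VAS, and the formula assumes equal variances. If EQ-VAS behaved as the DSI figures suggest, with r near 0.86, its gain too would be only about 7%.

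**Adjustment is not a complete or wholly free remedy.** This is correct. ANCOVA reduces the contribution of baseline noise without eliminating it, and corrects imbalance only as far as the measured baseline predicts follow-up. It uses one degree of freedom, which is negligible with about 105 patients (2 × 52.5).

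**Conclusion.** The point holds for EQ-VAS in Section 9.3.3, as avoidable loss of precision on a principal secondary outcome. The variance reduction available is 35% to 10% for r from 0.3 to 0.8. On the implied SD of 26.2 with 30% dropout, that would raise power from 65% to between 83% and 70%. These figures rest on an assumed r, equal variances at both visits, and an SD back-solved from the plan's own power claim.

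For DSI the point is one of ranking and consistency. A reader might apply the EQ-VAS range to DSI, or conclude that the trial's main power calculation suffers. The documents support neither: their SDs suggest a DSI gain of about 7%, and the sample size rests on a responder proportion.

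**What to change.** - **Section 9.3.3:** analyse follow-up EQ-VAS by ANCOVA with baseline EQ-VAS as covariate, or by one longitudinal model over 12, 26 and 52 weeks with visit-by-arm terms and baseline EQ-VAS. Keep the t-test on change as a sensitivity analysis.
- **Section 9.3.1:** name the baseline-adjusted model as the main analysis of mean DSI change, with the t-test or Mann-Whitney test as sensitivity.
- **Synopsis:** align the Brief Summary of Analysis with both.

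The cost is analysis-plan wording and one degree of freedom. No new data, visits or patients are needed. The change should be made before outcome data are examined by arm, so that the choice between adjusted and unadjusted results cannot depend on them.

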4.2.2 Principal Secondary Outcome

Change in generic HRQOL from baseline to 12, 26 and 52 weeks as assessed using the EuroQol (EQ) 5D-5LTM and EQ Visual Analogue Score (VAS) (Appendix B-2). This short self-administered generic tool consists of a descriptive system with 5 questions in 5-point Likert-type format, which assess how significantly the domains of mobility, self-care, usual activities, pain/discomfort and anxiety/depression are affected in daily life. The EQ-5D-5L Index, based on health state valuations elicited from the general public ^{54,55}, is anchored at 0.0 (dead) and 1.0 (full health). A minimum increment of 0.03 in the EQ-5D-DL index score can be considered clinically important as it corresponds to the smallest coefficient for a change from 'No problem' to 'Some problems' within a dimension of the EQ-5D-DL. The EQ VAS asks individuals to rate their current state of health from "worst imaginable" to "best imaginable" on a 100-point scale. ⁵⁶ EQ-5D-5LTM is brief and has been extensively validated in various populations and disease states. Normative data for Canadians and ESKD exist. ^{11,57}

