9.2 Sample Size and Power

Based on the limited literature published in this area, we expect an absolute difference of 25% between the intervention and control groups in the proportion of individuals in whom DSI severity score decreases by 7 points or more over time.

We predict DSI score will decrease in 50% of the intervention group and 25% of the control group at 12weeks (baseline prevalence of symptoms assumed to be 50%). A sample size of 58 patients in each arm will allow us to detect this difference with 80% power (alpha 0.05). We conservatively anticipate 30% dropout.⁸³ Therefore, a target sample size of 150 participants (75 participants per study arm) is proposed.

This sample size will allow us to detect a 7-point difference in mean change in DSI severity score using standard deviation of 16 with 80% power and alpha 0.05. This sample size (n=75 in each arm) will also provide 80% power with 0.05 alpha to detect a 12-point difference between groups in mean change in HRQOL measured using EQ-VAS (considered clinically important difference in other chronic diseases)⁸⁵ and a 30% absolute difference in proportion of individuals endorsing deficits in each domain of EQ5D-3L over time assuming 50% baseline deficit and development of new deficits in an additional 10% of the control group and a reduction in deficits in 15% of the intervention group.

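### The EQ-5D-5L index has no named analysis, and the only EQ-5D-5L test in 9.3.3 is a three-level new-deficit rule that counts no improvement

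*Combined protocol and SAP*

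**What the plan says.** Section 4.2.2 makes change in generic quality of life at 12, 26 and 52 weeks, assessed with the EQ-5D-5L and the EQ VAS, the principal secondary outcome. It describes the instrument as a "descriptive system with 5 questions in 5-point Likert-type format", introduces "The EQ-5D-5L Index, based on health state valuations elicited from the general public", and adds: "A minimum increment of 0.03 in the EQ-5D-DL index score can be considered clinically important".

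Section 9.3.3 gives the analyses. For the VAS: "Change in EQVAS over time will be compared between study groups using" a t-test. For the EQ-5D-5L it says that "we will compare the difference in proportion of individuals who develop new deficits (score of 2 or 3) in each domain of the EQ5D-5L over" follow-up. Neither the index nor the 0.03 appears in 9.2 or 9.3.3. A later sentence gives all other secondary outcomes whatever parametric or non-parametric test suits the data. Section 9.3.3 also sets two-sided p < 0.01 for all analyses.

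Section 9.2 states 80% power with 75 per arm, at alpha 0.05, for "a 30% absolute difference in proportion of individuals endorsing deficits in each domain of EQ5D-3L over time". It assumes 50% in deficit at baseline, a further 10% in the control arm and a reduction of 15% in the exercise arm. The form in Appendix 3.2 has five levels per domain.

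**The concern.** The outcome section and the analysis section describe different things. One gives a summary score with an important difference; the other gives a yes/no event per domain and never returns to the score.

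The event also fits the wrong instrument. Scores of 2 or 3 exhaust the deficits on a three-level scale, but on the form in use they leave out levels 4 and 5. The event counts worsening only, whereas section 2.2 hypothesises that exercise improves quality of life. Someone who moves from severe to slight problems adds nothing to the comparison. If 9.3.3 is followed as written, the EQ-5D-5L part of the principal secondary outcome rests on a test poorly placed to detect the benefit the trial expects, although the data for a better one are collected at every visit.

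**Working it through.** **1. The plan's own figure.** The rates in 9.2 are 50 + 10 = 60% (control) and 50 - 15 = 35% (exercise). That is a difference of 25 points, not 30. For a two-sided comparison of proportions,

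power = Φ[(Δ - 1.96·√(2·p̄(1-p̄)/n)) / √((p1(1-p1) + p2(1-p2))/n)], with p̄ = 0.475.

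- n = 75: (0.25 - 0.160)/0.0790 = 1.14, power 87%.
- n = 52 (75 × 0.70 = 52.5, after the 30% dropout in 9.2): (0.25 - 0.192)/0.0948 = 0.61, power 73%.
- A true 30-point difference gives about 96% at 75 and 88% at 52.

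None of these is the stated 80%. They also concern the prevalence of any deficit, which is not the event that 9.3.3 tests.

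**2. What the event counts.** A five-level item allows 5 × 4 = 20 changes of level, 10 of them improvements. Taking a new deficit to mean one that starts from level 1:

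- As worded (to level 2 or 3): 2 of 20.
- Read generously (to any level from 2 to 5): 4 of 20.
- Improvements counted: 0 of 10.
- People in deficit at baseline who can contribute: none, and 9.2 puts them at 50%.

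**3. Power per domain.** From the documents: 50% in deficit at baseline, then 60% v 35%; 52 evaluable per arm. Assumed, because the documents do not give them: baseline spread over levels 1 to 5 of 50/20/17/9/4%, and a correlation of 0.5 to 0.7 between visits. A latent normal variable is cut at that spread, and its follow-up mean is shifted in each arm to give 60% and 35% at level 2 or above. For the new-deficit rows, the denominator is everyone evaluable in the arm.

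| Analysis, two-sided 0.05 | Power |
|---|---|
| New deficit, level 2 or 3 (as worded) | 27-38% |
| New deficit, any level from 2 to 5 | 39-46% |
| Prevalence of any deficit at follow-up | 76-77% |
| Five-level score, adjusted for baseline level | 88-94% |

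The simulated 76-77% sits slightly above the 73% from the formula, which is an approximation. Restricting the denominator to people without a baseline deficit raises the first two rows by a few points and does not change the order.

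**4. Where the gain comes from.** Against the prevalence test, using the levels adds about 4-5 points when neither test is adjusted for baseline, and about 8-10 when both are. The rest is baseline adjustment.

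**5. At p < 0.01.** The rule as worded has 10-17%. The adjusted five-level score has about 73-84%, with the lower end nearer 70% in a repeat run.

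**6. The index at 0.03.** Power = Φ(0.03/(SD·√(2/n)) - 1.96). The documents give no SD, so a range is assumed. With n = 52, √(2/52) = 0.196:

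- SD 0.05: 3.06 - 1.96 = 1.10, power 86%.
- SD 0.10: 1.53 - 1.96 = -0.43, power 33%.
- SD 0.15: 1.02 - 1.96 = -0.94, power 17%.

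**The case against.** The best defence is that quality of life is not left to the domain test. EQ VAS comes first in 9.3.3, is analysed as a continuous score, and has in 9.2 its own 12-point important difference and power statement. That stands. A reader might infer that the whole principal secondary outcome rests on weak yes/no tests, or that 0.03 is the only important difference stated for it. The documents contradict both.

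Other parts of the defence also hold:

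- Section 4.2.2 says the outcome is assessed using the EQ-5D-5L. It describes the index but does not strictly define the outcome as the index.
- The general sentence in 9.3.3 on other secondary outcomes, or the mixed models in the synopsis, could be stretched to cover the index. So the index has no named analysis; it cannot be said that it will go untested. That is still thin for a principal secondary outcome, since no value set or model is given.
- It is tempting to say that any cut hides all movement among levels 2 to 5. That is true only of a cut between levels 1 and 2; a higher cut would register some of it.
- The whole gap between the prevalence test and the adjusted five-level score cannot be put down to the yes/no cut, as step 4 shows.
- The index is no cure-all. It has useful power for 0.03 only if its SD is small, and it dilutes an effect confined to one or two domains.

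None of this rescues the new-deficit rule. It mismatches the form and ignores improvement under either reading.

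**Conclusion.** The point holds for the EQ-5D-5L part of the principal secondary outcome and no further. The index and its 0.03 have no named analysis. The one named EQ-5D-5L analysis uses a three-level event on a five-level form and counts neither improvement nor anyone already in deficit. On the plan's rates with 52 per arm at two-sided 0.05, that means roughly 27-38% power per domain as worded, or 39-46% read generously, against 88-94% for the five-level score adjusted for baseline.

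The rates and dropout are the plan's; the level spread and visit correlation are assumptions. The adjusted analysis was simulated as a linear model on the level score, and an ordinal model was not simulated separately. The ranking, and the fact that improvement is ignored, matter more than the exact percentages. The documents do not support concluding that a real quality-of-life benefit would be missed altogether, because the EQ VAS comparison remains.

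**What to change.** In 9.3.3:

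- Replace the new-deficit test with an analysis of each domain on its five levels at 12, 26 and 52 weeks, using an ordinal model adjusted for the baseline level.
- Keep the proportion with any problem (level 2 or above) as a descriptive table.
- Name an analysis of the EQ-5D-5L index, with one stated value set and a model adjusted for baseline index. Report the estimate and confidence interval against 0.03, and claim no power for 0.03.

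In 9.2, remove the EQ5D-3L domain power sentence, or correct both the instrument and the 25 v 30 point discrepancy.

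The cost is SAP wording and the choice of a value set; no new data are needed. The drawback is the dilution of the index when only one or two domains respond, which the domain models cover.

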2.1.3 Reduced symptom burden may be a major driver of improved HRQOL in ESKD

Not surprisingly, increased symptom burden is strongly associated with poor HRQOL and low functional status in individuals on HD. In 120 individuals within 3 months of commencing HD, greater symptom burden was associated with lower HRQOL as measured by the physical and mental components scores of the Short Form 36 (SF-36). Using the DSI, Weisbord et al demonstrated that the burden of mental and physical symptoms in HD patients were independently associated with poor HRQOL measured using the Illness Effects Questionnaire (r=0.6 and 0.61, respectively). Finally, in a cohort of 301 Chinese HD patients with heavy symptom burden as measured by DSI, symptom burden was strongly correlated with reduced HRQOL as measured using the SF-36 (rs = -0.619; p<0.001).

Several recent systematic reviews of exercise programming in HD have demonstrated improvement in HRQOL as measured by generic self-reported instruments.^{14, 34} It is plausible that improved symptom control is a major driver of the improvement seen in HRQOL after exercise participation in this population. However, only a single study has investigated the effect of exercise on dialysis-related symptom burden using a questionnaire with limited previous validation and showed no benefit.²⁵ Using validated measurement tools for symptom burden and HRQOL with extensive previous use (DSI and EuroQol-5D3L respectively), we hope to further characterize the role of symptom burden in the improvements to HRQOL seen with exercise in the HD population.

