Appendix 3.2 EuroQol 5D-5L Health-Related Quality of Life Questionnaire

Health Questionnaire

English version for Canada

[figure not shown]
Canada (English) © 2009 EuroQol Group EQ-5D™ is a trade mark of the EuroQol Group

MOBILITY I have no problems in walking about I have slight problems in walking about I have moderate problems in walking about I have severe problems in walking about I am unable to walk about SELF-CARE I have no problems washing or dressing myself I have slight problems washing or dressing myself I have moderate problems washing or dressing myself I have severe problems washing or dressing myself I am unable to wash or dress myself **USUAL ACTIVITIES** (e.g. work, study, housework, family or leisure activities) I have no problems doing my usual activities I have slight problems doing my usual activities I have moderate problems doing my usual activities I have severe problems doing my usual activities I am unable to do my usual activities **PAIN / DISCOMFORT** I have no pain or discomfort I have slight pain or discomfort I have moderate pain or discomfort I have severe pain or discomfort I have extreme pain or discomfort **ANXIETY / DEPRESSION** I am not anxious or depressed I am slightly anxious or depressed I am moderately anxious or depressed I am severely anxious or depressed

Under each heading, please tick the ONE box that best describes your health TODAY.

- We would like to know how good or bad your health is TODAY.
- This scale is numbered from 0 to 100.
- 100 means the best health you can imagine.
 0 means the worst health you can imagine.
- Mark an X on the scale to indicate how your health is TODAY.
- Now, please write the number you marked on the scale in the box below.

YOUR HEALTH TODAY =

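### The EQ-5D-5L new-deficit rule in section 9.3.3 counts only scores 2 and 3 on a five-level form, and the section 9.2 power statement for these domains gives 30% where its own inputs give 25 points

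*Combined protocol and SAP*

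**What the plan says.** Section 9.3.3 plans, besides a t-test on EQ-VAS, a between-group comparison of the proportion who "develop new deficits (score of 2 or 3) in each domain of the EQ5D-5L over time".

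The synopsis, the procedures list in 7.1 and the schedule in 7.3 all name the five-level instrument. Section 4.2.2 describes it as "a descriptive system with 5 questions in 5-point Likert-type format". The mobility item in Appendix 3.2 offers five ordered options: none, slight, moderate, severe ("I have severe problems in walking about") and unable.

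The three-level version survives elsewhere. Section 2.1.3 refers to "extensive previous use (DSI and EuroQol-5D3L respectively", and Appendix 1 lists only the three-level abbreviation. Section 9.2 says that 75 per arm gives 80% power at alpha 0.05 to detect "a 30% absolute difference in proportion of individuals endorsing deficits in each domain of EQ5D-3L". Its assumptions are a 50% baseline deficit, "development of new deficits in an additional 10% of the control group and a reduction in deficits in 15% of the intervention group".

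**The concern.** A 2-or-3 rule captures every deficit on a three-level form. On a five-level form it leaves two problem levels uncounted. A programmer who follows 9.3.3 literally would record a participant who goes from no problems to slight problems as having a new deficit, and one who goes from no problems to unable as having none. If the arms differ in how often participants reach the worst levels, the comparison could be distorted in either direction, and the events lost are the most serious ones.

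The power statement for the same domains raises a second question. Its stated difference does not follow from its stated rates, it names the other version of the instrument, and it describes a different quantity from the one that 9.3.3 tests.

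**Working it through.** **Scoring rule**

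Five levels per domain means one level without problems and four with problems. Two score values cannot cover four levels, whatever the coding:

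- Coded 1 to 5 in printed order: 2 and 3 are slight and moderate. The moves 1 to 4 and 1 to 5 are missed.
- Coded in reverse: 2 and 3 are severe and moderate. The worst level and the slight level are missed.

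The first coding is the natural one, and the use of a numeric score in 9.3.3 implies some numbering. No section extends the rule to levels 4 and 5. The documents give no distribution of participants over levels, so the number misclassified cannot be calculated.

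**Power statement in 9.2**

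Inputs, all from 9.2: baseline deficit 50%; control +10%; intervention −15%; 75 per arm; alpha 0.05; power 80%. Sidedness is not stated for this figure, so two-sided is assumed.

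*Method check.* Use the two-proportion formula with pooled variance under the null and no continuity correction:

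n = [1.96 × √(2p̄(1−p̄)) + 0.8416 × √(p1(1−p1) + p2(1−p2))]² / (p1−p2)²

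For the primary responder rates of 50% and 25% it gives [1.96 × √0.46875 + 0.8416 × √0.4375]² / 0.0625 = 57.7, so 58 per arm. This is the plan's own figure.

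*Stated difference.* Control 50 + 10 = 60%; intervention 50 − 15 = 35%; difference 60 − 35 = 25 points. Read as relative changes, the rates are 50 × 1.10 = 55% and 50 × 0.85 = 42.5%, a difference of 12.5 points. Neither reading gives the stated 30.

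*Power at 75 per arm, alpha 0.05.* Power = Φ{[|p1−p2| − 1.96 × √(2p̄(1−p̄)/n)] / √([p1(1−p1) + p2(1−p2)]/n)}

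- 60% against 35%: (0.25 − 1.96 × √(0.49875/75)) / √(0.4675/75) = (0.25 − 0.1598) / 0.0790 = 1.14, so power is 87.3% (83.5% with continuity correction).
- 60% against 30%: (0.30 − 1.96 × √(0.495/75)) / √(0.45/75) = (0.30 − 0.1592) / 0.0775 = 1.82, so power is 96.5% (95.0% with continuity correction).

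For 80% power at alpha 0.05, 25 points would need 62 per arm and 30 points (60% against 30%) would need 42. With 75 per arm, 80% power corresponds to a difference of about 22.7 points below 60%.

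**What is powered and what is tested**

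Section 9.2 concerns the proportion endorsing a deficit, which is a prevalence. Section 9.3.3 compares the proportion developing a new deficit, which is an incidence. Section 9.2 gives a net reduction for the intervention arm and no rate of new deficits there, so power for the planned comparison cannot be computed from the documents.

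**The case against.** The rule looks like a leftover from the three-level version, and a competent analyst would probably count levels 4 and 5 anyway. Section 4.2.2 does not name per-domain new deficits, and it gives an importance threshold only for the index. The 9.2 statement does not drive the sample size. These points limit the weight of the issue. They do not remove it, because the written rule is what would be programmed and nothing in the plan overrides it. It is also fair that *new* most naturally means absent at baseline, since 4.2.2 defines the outcome as change from baseline. Stating that condition only makes explicit what is probably intended.

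A reader might be tempted to go further in three ways.

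- *The domain test is underpowered.* One could apply the threshold in 9.3.3 ("For all analyses, two-sided p < 0.01 will be statistically significant") or the attrition in 9.2 ("We conservatively anticipate 30% dropout") to 60% against 35%. The documents do not support this. 9.3.3 plans no test of that prevalence contrast, and it leaves open how 0.01 relates to the Bonferroni adjustment mentioned in the same section. 9.2 ties its statement to 75 per arm, and 9.3.1 and 9.3.4 call for multiple imputation once missing outcomes exceed 25%, so a completers-only figure would not describe the planned analysis.
- *The 80% power claim is false.* It is not: at the n and alpha that 9.2 states, both 25 and 30 points exceed 80%.
- *The unstated denominator biases the result.* Taking all participants or only those without a deficit at baseline rescales both arms alike when baseline rates are equal. This is missing detail that should be stated; no bias has been shown.

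**Conclusion.** Two corrections are warranted.

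First, the new-deficit rule in 9.3.3 does not fit the five-level form. With coding 1 to 5 in printed order, which is inferred, it omits moves from no problems to the two worst levels. The number of participants affected and the direction of any distortion cannot be determined from the documents.

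Second, 9.2 does not agree with itself: 30 is stated, and 25 points follows from its rates read as absolute changes. At 75 per arm and two-sided alpha 0.05, power is about 87% for 25 points and about 97% for 30, so the claim of 80% is met but does not match either difference. The statement also names the three-level form and addresses prevalence, so it is not the power of the comparison in 9.3.3, for which no power can be derived.

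The effect is confined to the per-domain EQ-5D comparison and its power statement. The DSI primary outcome, EQ-VAS, the EQ-5D-5L index and the sample size of 150, which rests on the DSI responder calculation, are untouched.

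**What to change.** In 9.3.3, replace the 2-or-3 rule with: level 2, 3, 4 or 5 at follow-up in a participant at level 1 at baseline. The sponsor should state the denominator for the proportion. Worsening in someone who already has a deficit (for example from 2 to 5) stays outside a new-deficit comparison.

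In 9.2, either replace the 30% with 25 points (60% against 35%) or correct the input rates. Name the EQ-5D-5L, and confirm that the 50% baseline rate, stated for the three-level form, holds for the five-level one. Say that the figure concerns any deficit (levels 2 to 5) and is not the power of the new-deficit comparison in 9.3.3.

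Correct the instrument name in 2.1.3 and Appendix 1 as an editorial matter.

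The cost is wording only: no new data and no added tests. The definition should be fixed before analysis, so that it is not chosen with the results in view.
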